11.5 SAFETY ANALYSIS

All safety analyses will be performed on the ITT population based on all available data.

11.5.1 ADVERSE EVENT

Adverse events (AEs) will be classified as intraoperative or postoperative. The number and the percent of eyes reporting at least 1 adverse event of a given type will be summarized. Additionally, the number of reports of each type of AEs will be provided.

For each AE, the number and the percent of eyes reported with the event will be summarized by the severity level. For eyes with multiple reports of the same type of AE, the maximum severity will be used. Similarly, the AE relationship to the procedure will be summarized. For eyes with multiple reports of the same type of AE, the closest relationship to the procedure will be used.

11.5.2 BEST CORRECTED VISUAL ACUITY (BCVA)

The number and percent of eyes reporting with BCVA of 20/20 or better, 20/25 or better, 20/32 or better, 20/40 or better, worse than 20/40 to 20/80, worse than 20/80 to 20/200, and worse than 20/200 at each visit will be summarized. The number and

percent of eyes reporting BCVA of increase \geq 10 letters, increase 10 letters, increase \geq 5 letters to < 10 letters, within 5 letters change, decrease \geq 5 letters to < 10 letters, decrease 10 letters, and decrease \geq 10 letters at each postoperative visit will be calculated.

11.5.3 OTHER SAFETY OUTCOMES

The number and percent of eyes reported with each kind of slit lamp findings, gonioscopy findings, and dilated fundus examination findings at each visit will be provided.

The descriptive statistics for the continuous variables will be derived for the visual field mean deviation (MD) and pattern standard deviation (PSD).

11.6 INTERIM ANALYSES

The primary analysis for this study will occur after the final subject reaches their 12-month follow-up. Endpoints listed below will be analyzed at an interim analysis performed when at least 50% subjects complete 6 month follow-up and when 100% patients complete 6 month follow-up.

Effectiveness endpoints:

1. Reduction in mean IOP from screening visit; and
2. Reduction in mean number of IOP-lowering medications from screening visit
3. Percent of eyes with a \geq 20% reduction in IOP with no increase in IOP-lowering medications compared to screening visit
4. Percent of eyes with IOP between 6 and 18 mmHg with no increase in IOP-lowering medications compared to screening visit

Safety endpoints:

1. Rates of ocular adverse events (intraoperative, postoperative)
2. Reduction in best corrected visual acuity (BCVA) from baseline (note: reduction in BCVA due to PCO will not be treated as a safety event)

It is noteworthy that the two interim analyses are based on the 6-month measurements, not the washout IOP at 12 months for the primary and secondary effectiveness endpoint. Additionally, the interim analyses are not for claiming effectiveness of the study device and the study will not be terminated due to the 6-month outcomes. Therefore, the study p-values are not adjusted for the planned interim analyses.

11.7 DEVIATION FROM THE STATISTICAL PLAN

Any deviations from the statistical plan will be noted in the final report.

12 MONITORING PROCEDURES

Sight Sciences or contract research organization (CRO) personnel will monitor the study in a manner consistent with FDA regulations, good clinical practices and the clinical research standards adopted by Sight Sciences. Study monitoring will involve the following elements:

- Site Qualification: Sight Sciences or CRO personnel will meet with investigators and clinical study staff prior to the initiation of the study in order to review the adequacy of the subject population, facilities, and equipment with respect to the needs of the study, and to familiarize the investigator with the study protocol. If Sight Sciences or the CRO have recently been involved with an investigator for another study, a site qualification visit may not be necessary.
- Site Initiation: Sight Sciences and/or CRO personnel will meet with the investigator(s) and clinical study staff when the site is ready to begin enrolling subjects in order to train them in how to properly select subjects, perform the study procedure, and record study data. This visit will include, but not be limited to a review of the following:
 - Detailed review of the protocol
 - Informed consent procedures
 - Instructions for the surgical procedure
 - Records and reports
- Interim Monitoring: Sight Sciences or CRO personnel will visit the clinical site routinely during the study to review charts and to perform source document verification, to ensure proper adherence to the study protocol, and to review regulatory documents. Interim monitoring visits and telephone consultation will occur as necessary during the course of the study to ensure the proper progress and documentation of the study findings.
- Study Closure: At the conclusion of the trial there will be a study closure visit during which several actions, including but not limited to the following, will be performed:
 - A final inspection of the study binder
 - Accountability and return of all devices and study materials to the sponsor
 - Discussion of record retention requirements with the investigator
 - Close-out notification to the IRB

13 DATA AND QUALITY MANAGEMENT

13.1 DATABASE MANAGEMENT

The study database will be designed using an electric data capture (EDC) system that is compliant with 21 CFR Part 11 and relevant guidance documents. The EDC will be developed and maintained by an independent, qualified data management firm.

The database will incorporate time-stamped audit trails, protection of human subjects, restricted access, and data security at the component level. Each database module, including each individual eCRF, will be validated by conducting a series of standard tests that demonstrate usability and correctness of the database system. The database will be maintained on an ongoing basis and will be routinely backed up.

13.2 SUBJECT IDENTIFICATION

The subjects will be identified by a five-digit subject number composed of a one-digit study identification number, a two-digit center identification number followed by a two-digit sequential subject number. The subject identification will be assigned when informed consent is obtained. In this way, information contained in the study records will be kept as confidential as possible.

13.3 SUBJECT ACCOUNTABILITY

All subjects enrolled and treated in this clinical investigation shall be monitored for the duration of the investigation. The clinical investigation shall be considered completed when all subjects that have been enrolled in the investigation have reached the final reporting period, excluding subjects who were withdrawn.

13.4 CONFIDENTIALITY

All medical records associated with the clinical investigation will be made available for review by Sight Sciences personnel, its contract research organization (CRO) and governmental/regulatory agencies involved. The results of the study may be published in the future for scientific and marketing purposes, but the identity (name) of each subject will not be revealed. All records will be stored in a secure area at the investigator's facility, the CRO, the data management firm and at Sight Sciences, Inc.

13.5 SOURCE DATA AND CASE REPORT FORMS

Source data will be entered into a validated electronic system at each site by trained personnel in accordance with 21 CFR Part 11 requirements. Electronic entries will be 100% verified against corresponding source data at the sites and queried/corrected if needed to the extent possible. Medical site records serve as source data. In addition,

data that are collected exclusively for the purpose of this study and not normally recorded in the subjects' medical records can be collected directly on the study worksheets provided by the sponsor and these study worksheets will serve as the source data.

Source data and study worksheets are to be maintained at the site in the subject records or in the medical records. All entries must be made in black or blue ink and changes must be made by strike-through only with date and initials or signature. All source documents must be completed and signed by the authorized study personnel (e.g., study coordinator). No "white-out" is to be used on the source documents.

13.6 RETENTION PERIOD

Clinical sites are to retain any and all clinical trial material (documentation, photographs, etc.) for a period of two years from the date a marketing application is approved or two years after the investigation has been discontinued, or as directed by their institutional document retention requirements, whichever is the longest. After that time, the items must be returned to Sight Sciences for archiving. Unused medical devices are to be returned to the sponsor at the conclusion of the enrollment period.

14 PROTOCOL MODIFICATIONS AND DEVIATIONS

Protocol modifications may occur during the study. Each will be approved by the sponsor before implementation. Each will undergo Institutional Review Board (IRB) review and approval, as necessary.

Any deviations from this protocol intended to protect the life or physical well-being of a subject in an emergency are to be reported to Sight Sciences, Inc. as well as the IRB as soon as possible, and no later than 5 working days after the emergency occurred.

All protocol deviations will be documented using the Protocol Deviation form.

15 DEVICE FAILURES AND MALFUNCTIONS

All device failures or malfunctions should be recorded on the Device Deficiency Form and reported to Sight Sciences Customer Service [REDACTED]

16 ETHICAL CONSIDERATIONS

16.1 DECLARATION OF HELSINKI

This study shall be conducted in accordance with the Declaration of Helsinki (Appendix D).

16.2 INSTITUTIONAL REVIEW BOARDS (IRB)

The study shall not begin at a site until approval has been obtained from the reviewing IRB. It is the Investigators' responsibility to obtain and maintain written approval of the study protocol and Informed Consent documents from the appropriate IRB. It is also the Investigators' responsibility to notify that body about any amendments to these documents and to follow the IRBs rules regarding the reporting of Adverse Events and Protocol Deviations related to the device and/or this study. Copies of all written approvals (identifying the study, the submitted and approved documents and the date reviewed) and the approved versions of the documents must be provided to Sight Sciences or its CRO.

The Investigators must file all correspondence with the IRB and forward copies of such correspondence to Sight Sciences.

16.3 INFORMED CONSENT FORM (ICF)

An Informed Consent template that covers all protocol procedures and follows GCP Guidelines will be prepared by Sight Sciences and made available to each Investigator. The Investigator may adapt these templates to the requirements of the local IRB and of the institution where the study is conducted, but any revisions made to the ICF must be submitted to the sponsor for review prior to submission to the IRB. A copy of each IRB-approved ICF version is to be made available to Sight Sciences and its CRO. The approved, IRB-stamped ICF is to be kept in its full length in the study Regulatory Binder. Original, signed ICFs are to be maintained in the subject's study records and must be made available for monitoring review.

16.4 PUBLIC LISTING OF STUDY

The study will be listed on the NIH website www.clinicaltrials.gov.

17 STUDY ADMINISTRATION

17.1 EARLY TERMINATION OR SUSPENSION OF THE STUDY OR AN INVESTIGATIONAL SITE

Sight Sciences may terminate the study, in which case the investigators and associated IRBs will be notified in writing. Possible reasons for study termination include but are not limited to:

- The discovery of an unexpected, significant, or unacceptable risk to the study subjects implanted with the device
- Withdrawal of FDA clearance of the OMNI device.
- Insufficient enrollment in the study

Sight Sciences reserves the right to stop the study at a particular site any time after the initiation visit if there have been no subject enrollments or if there have been significant protocol deviations/violations at the site.

Likewise, a principal investigator may terminate the study at his/her institution. This decision must be followed by written notification to Sight Sciences within five working days, stating the reasons for termination.

If the study is terminated, every effort should be made to obtain final follow-up from all subjects.

In the event that there are significant human use issues with the device, the investigator will be consulted to make a determination of whether the study should be terminated or not.

17.2 INVESTIGATOR RESPONSIBILITIES

17.2.1 GENERAL RESPONSIBILITIES OF INVESTIGATORS

An Investigator is responsible for ensuring that an investigation is conducted according to the signed agreement, the investigational plan and applicable FDA regulations, for protecting the rights, safety, and welfare of subjects under the Investigator's care, and for the control of devices under investigation. An Investigator also is responsible for ensuring that informed consent is obtained in accordance with 21 CFR part 50.

17.2.2 SPECIFIC RESPONSIBILITIES OF INVESTIGATORS

1. Awaiting approval - An Investigator may determine whether potential subjects would be interested in participating in an investigation, but shall not request the written informed consent of any subject to participate, and shall not allow any subject to participate before obtaining IRB approval.

2. Subject Qualification -The Investigator is responsible for ensuring that all subjects entering the study conform to the subject selection criteria.
3. Compliance - An Investigator shall conduct an investigation in accordance with the signed agreement with the Sponsor, the investigational plan, all applicable FDA regulations, and any conditions of approval imposed by an IRB.

17.2.3 INVESTIGATOR RECORDS

A participating Investigator shall maintain the following accurate, complete, and current records relating to the Investigator's participation in an investigation for the period specified in Section 13.6:

1. All correspondence with another Investigator, an IRB, the Sponsor, a monitor, or FDA, including required reports.
2. Records of each subject's case history and exposure to the device. Case histories include the study CRF's/worksheets and supporting data including, for example, signed and dated consent forms and medical records. Such records shall include:
 - a) Documents evidencing informed consent.
 - b) All relevant observations, including records concerning adverse device effects (whether anticipated or unanticipated), information and data on the condition of each subject upon entering, and during the course of, the investigation, including information about relevant previous medical history and the results of all diagnostic tests.
3. The protocol, with documents showing the dates and reasons for each deviation from the protocol.
4. Any other records that FDA requires to be maintained by regulation or by specific requirement for a category of investigations or a particular investigation.

17.2.4 INVESTIGATOR REPORTS

An Investigator shall prepare and submit the following complete, accurate, and timely reports:

1. Unanticipated Adverse Device Effects - An Investigator shall submit to the Sponsor and to the reviewing IRB a report of any unanticipated adverse device effect occurring during an investigation as soon as possible, but in no event later than 10 working days after the Investigator first learns of the effect.
2. Withdrawal of IRB Approval - An Investigator shall report to the Sponsor, within 5 working days, a withdrawal of approval by the reviewing IRB of the Investigator's part of an investigation.

3. Progress - An Investigator shall submit progress reports on the investigation to the Sponsor, the monitor, and the reviewing IRB at regular intervals, but in no event less often than yearly.
4. Deviations from the Investigational Plan - An Investigator shall document and report to the Sponsor any deviation from the investigational plan.
5. Informed Consent - If an Investigator enrolls a subject without obtaining informed consent, the Investigator shall report such use to the Sponsor and the reviewing IRB within 5 working days after the use occurs.
6. Final Report - An Investigator shall, within 3 months after termination or completion of the investigation or the Investigator's part of the investigation, submit a final report to the Sponsor and the reviewing IRB.
7. Other - An Investigator shall, upon request by a reviewing IRB or FDA, provide accurate, complete, and current information about any aspect of the investigation.

17.3 INVESTIGATOR AGREEMENT

The principal investigators in each center shall agree to the clinical protocol and any amendments and indicate their approval and agreement by signing and dating the cover page of the study protocol and the Investigator Responsibility Agreement.

18 PUBLICATION POLICY

Sight Sciences recognizes the value of disseminating research results. It is understood that the Study is part of the Multi-Center Clinical Trial and publication of results is expected. This publications policy applies to journal articles, conference abstracts, and conference presentations (posters and slides) covering Sight Sciences-sponsored clinical studies. This policy is in addition to any arrangement contained in the Clinical Trial Agreement between Sight Sciences and the investigator.

Multi-Site Data

Clinical site investigators are encouraged to propose publications and abstracts that include clinical or research data from multiple clinical sites; such projects will be coordinated by Sight Sciences. Authorship of papers and abstracts resulting from these projects will be determined collaboratively according to the following guidelines:

- The first author on such publications will be the person who primarily wrote the paper and took the lead on the research. In the case of clinical trial papers where all authors contributed equally, authorship order may be based on site enrollment or other criteria at Sight Sciences' discretion.
- Other authors include those who significantly contributed to the specific work.
- At least one person from each clinical site whose study subjects appear in the work will be acknowledged in the manuscript/presentation in some way, either

as an author group member, a non-author contributor, or listed in the acknowledgements, depending on the particular policies of the journal or conference.

Single Site Data

After publication of the multi-center study results in a peer-reviewed journal, or if Sponsor has not submitted a manuscript for publication in a peer-reviewed journal within twelve (12) months after the study has been completed, whichever occurs first, Investigators may publish the results of the Study generated by the Investigator, subject to the obligations of the Clinical Trial Agreement between Sight Sciences and the Investigator, and the prior approval of Sponsor in writing.

Publications Review Policy

Investigators must submit all presentations, posters, abstracts and manuscripts pertaining to this study to Sight Sciences for review in advance of their submission. Sight Sciences conducts this review to protect its proprietary rights to information, inventions, or products developed under the Study. Please use the following guideline to determine the absolute minimum advance time for submitting an item to Sight Sciences for review:

- Presentations/Posters: 5 business days in advance of presentation
- Abstracts: 5 business days in advance of submission
- Manuscripts: 30 calendar days in advance of submission for publication

In accordance with the Clinical Trial Agreement, these items must receive written approval from Sight Sciences in order for them to be submitted or presented. If an item is not received in the timeframe listed above, approval may not be granted due to insufficient time for considered review. In addition, since most of our Clinical Trial Agreements require that Sight Sciences has 60 days to review publications, Sight Sciences reserves the rights granted in those Agreements if circumstances require a longer review.

20 APPENDIX A – METHODS FOR EXAMS, TESTS AND QUESTIONNAIRES

20.1 LIST OF STUDY PROCEDURES

1. Informed Consent
2. Demographics, Medical & Ocular History
3. Medication Log
4. BCVA
5. Visual Field (Humphrey 24-2 SITA)
6. IOP (Goldmann Tonometry)
7. Unmedicated Diurnal IOP
8. Slit Lamp Exam
9. Gonioscopy
10. Dilated Fundus Exam/C:D Ratio
11. Eligibility Assessment
12. Cataract Extraction + ab-interno transluminal viscoelastic delivery + Trabeculotomy
13. AE Assessment

20.2 SEVERITY OF GLAUCOMA

Severity of glaucoma is graded as documented in subjects' medical charts using the coding guidelines shown in Figure 3.

Figure 3: AAO/AGS/ICD-10 Glaucoma Stage Definitions

[figure not shown]

GLAUCOMA STAGE DEFINITIONS

Mild or Early Stage Glaucoma

ICD-10 7th digit "1"

[figure not shown]
- Optic nerve abnormalities consistent with glaucoma
- but NO visual field abnormalities on any visual field test
- OR abnormalities present only on short-wavelength automated perimetry or frequency doubling perimetry

Moderate Stage Glaucoma

ICD-10 7th digit "2"

[figure not shown]
- Optic nerve abnormalities consistent with glaucoma
- AND glaucomatous visual field abnormalities in ONE hemifield and
- NOT within 5 degrees of fixation (note: 5 degrees = involvement of spots nearest fixation)

Advanced, Late, Severe Stage

ICD-10 7th digit "3"

- Optic nerve abnormalities consistent with glaucoma
- AND glaucomatous visual field abnormalities in BOTH hemifields
- AND/OR loss within 5 degrees of fixation in at least one hemifield

Indeterminate Stage

ICD-10 7th digit "4"

- Visual fields not performed yet
- Patient incapable of visual field testing
- Unreliable/uninterpretable visual field testing

Unspecified

ICD-10 7th digit "0"

- Stage not recorded in chart
- Remember to document stage in record!

ICD-10

For ICD-10, not all glaucoma diagnoses require the use of Staging at the 7th digit.

These are the Codes in ICD-10 that do not have a laterality digit: Code the Stage for the most severely affected eye, if required in the 7th digit.

- Unspecified open-angle glaucoma H40.10- (Requires Stage digit for most severely affected eye)
- Unspecified primary angle-closure glaucoma H40.20- (Requires Stage digit for most severely affected eye)
- Other specified glaucoma H40.89 (Stage is not used)
- Unspecified glaucoma H40.9 (Stage is not used)

Risk Factors for OAG Suspect Codes

- African American or Hispanic race
- Family history of glaucoma in 1st degree relative
- Thin central corneal thickness
- High IOP
- Pseudoexfoliation or pigment dispersion syndrome

≥ 3 risk factors = high risk
≤ 2 risk factors = low risk

20.4 VISUAL ACUITY

ETDRS Testing Method

Best-corrected visual acuity at Baseline and all scheduled follow-up visits will be measured using the ETDRS charts at 1 or 4 meters.

The ETDRS chart must be placed at a distance of 4.00 meters (13 feet and 1.5 inches, or 157.5 inches) from cornea to chart surface, when using a 4-meter chart. For the patients unable to read the topmost line of 4.00 meter chart VA testing should be done using 1 meter chart. For testing at 1 meter, the distance must be 1.00 (39 and 3/8 inches). A measuring tape or meter stick should always be available to verify the chart distance, even if the examining chair is supposed to be immovable or if reference marks are placed on the floor or walls. (Custodial and other staff have been known to move room furnishings about and clean-off marks from the floor or wall while performing their duties, necessitating re-establishing the correct distances for the lane.)

The 1-meter distance is measured from the eye of the participant, seated comfortably in a chair with his/her back firmly placed against the chair, to the center of the 2nd or 4th letter of the 3rd line of the chart. The measuring device can be homemade (e.g., a dowel rod accurately cut to a length of 1.00 m) or 1 meter ruler may be purchased.

Note: If it is necessary to refract at the 1-meter distance, remember to add +0.75 sphere to the trial frame. Subtract the +0.75 sphere from the final refraction obtained at the 1-meter distance before recording the refraction on the form.

Methods

The subject should attempt to read each letter, line-by-line, left to right, beginning with line 1 at the top of the chart. The subjects should be told that the chart has letters only, no numbers. If the subject reads a number, he or she should be reminded that the chart contains no numbers, and the examiner should then request a letter in lieu of the number. The subject should be asked to read slowly, about one letter per second, so as to achieve the best identification of each letter. He/she is not to proceed to the next letter until he/she has given a definite response.

A maximum effort should be made to identify each letter on the chart. When the subject says he/she cannot read a letter, the subject should be encouraged to guess. If the subject identified two (2) letters (e.g., A or B), the subject should be asked to choose one letter and, if necessary, to guess. When it becomes evident that no further meaningful readings can be made despite encouragement to read or guess, the examiner should stop the testing for that eye. However, all letters on the last line should be attempted as letter difficulties vary and the last letter may be the only one read correctly. The number of letters missed or read incorrectly should be noted.

In order to provide standardized and well-controlled assessment of visual acuity, all visual acuity assessments for a subject should be performed consistently (e.g., the same lighting conditions, viewing distance, etc.) at each visit.

Recording and Scoring Best-Corrected Visual Acuity

Using the Visual Acuity Worksheet, circle each letter the subject identifies correctly, write total correct for each row in the place provided, and compute the total correct for all rows. Do not mark letters read incorrectly or not read at all. Each letter read correctly is recorded as one. Only move to the next line if 4 or more letters are read correctly.

The number of correct letters will be recorded on the study worksheets and entered into the EDC.

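### Section 20.4 enters 1 m and 4 m ETDRS letter counts as if they were on one scale, so some eyes that change test distance get the wrong BCVA change

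*Combined protocol and SAP*

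**What the plan says.** Section 20.4 (Appendix A) allows two test distances: "Best-corrected visual acuity at Baseline and all scheduled follow-up visits will be measured using the ETDRS charts at 1 or 4 meters". The change of distance is triggered by the top line: "For the patients unable to read the topmost line of 4.00 meter chart VA testing should be done using 1 meter chart".

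Scoring is the same at both distances. "Each letter read correctly is recorded as one", the examiner is to "compute the total correct for all rows", and "The number of correct letters will be recorded on the study worksheets and entered into the EDC". The section does correct the refraction for the shorter distance ("remember to add +0.75 sphere to the trial frame", removed again before the refraction is recorded), but nothing corrects the letter score. The text does not say that the test distance is entered with the count.

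The same section also asks that a subject's acuity tests be done under constant conditions at each visit, and names viewing distance as one of them.

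The counts are used in three places:
- Section 7.2 makes reduction in BCVA from baseline a safety endpoint.
- Section 10.2 lists a loss of 10 or more letters at or after 3 months as an anticipated adverse event.
- Section 11.5.2 tabulates bands of letter change, with outer bands at 10 letters, and Snellen categories down to worse than 20/200.

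None of the three gives a conversion.

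**The concern.** Moving an eye from 4 m to 1 m helps only if the letters then subtend a larger angle. A 1 m chart rescaled to the same angles would defeat the same eye again, and the rule would serve no purpose. A given count at 1 m therefore stands for worse vision than the same count at 4 m, yet the scoring rule treats the two as equal.

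An eye that crosses the top-line limit between visits then gets a wrong change score. If it worsens, a real loss can be hidden. If it improves, as it may once the cataract is out, a real gain can be recorded as a loss. Serious loss of vision is a rare event that the safety tables exist to show, so a single wrong eye matters more here than in an average.

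**Working it through.** **Inputs from section 20.4.** "The ETDRS chart must be placed at a distance of 4.00 meters (13 feet and 1.5 inches, or 157.5 inches") and "For testing at 1 meter, the distance must be 1.00 (39 and 3/8 inches"). The plan states no offset, so there is no figure to reproduce. Its distances are consistent: 13 × 12 + 1.5 = 157.5 in, 157.5 / 39.375 = 4.000, and 1/1 − 1/4 = 0.75 dioptre, which matches the stated sphere correction.

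**Assumptions, not stated in the documents.**
- The chart layout is the same at both distances.
- Each line has 5 letters. The rule for moving to the next line asks for 4 or more correct, so a line has at least 4; the range is 4 to 5.
- Each line is a step of 0.1 log unit. The 20/20, 20/25, 20/32 and 20/40 categories in 11.5.2 are steps of 0.097, 0.107 and 0.097, which supports this.

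**Offset.** Letters per line × log10(4) / step = 5 × 0.602 / 0.1 = 30.1 letters. With 4 letters per line, 4 × 0.602 / 0.1 = 24.1. The rest uses 30.

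**Highest possible 1 m count.** An eye sent to 1 m has failed the 4 m top line, so it would read about 0 to 4 letters at 4 m. Its 1 m count is then at most about 30 to 34.

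**Worsening, 4 m to 1 m.** Recorded change = true change + 30. With a 1 m count of at most 34, an eye that had 34 + 10 = 44 or more letters at 4 m always records a loss of at least 10. Only an eye with a 4 m count below about 44 can be missed, and then only if its true loss is below 10 + 30 = 40 letters.

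**Improving, 1 m to 4 m.** Recorded change = true change − 30. A recorded loss of 10 or more needs a 4 m count of at most 34 − 10 = 24.

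| Earlier count | Later count | Recorded change | Change on one scale (4 m count + 30) | Effect |
|---|---|---|---|---|
| 25 at 4 m | 25 at 1 m | 0 | 25 − 55 = −30 | loss missed |
| 40 at 4 m | 25 at 1 m | −15 | 25 − 70 = −45 | flagged, size wrong |
| 44 at 4 m | 34 at 1 m | −10 | 34 − 74 = −40 | flagged, size wrong |
| 30 at 1 m | 20 at 4 m | −10 | 50 − 30 = +20 | false loss |
| 30 at 1 m | 30 at 4 m | 0 | 60 − 30 = +30 | gain missed, no false loss |
| 34 at 1 m | 44 at 4 m | +10 | 74 − 34 = +40 | band right, size wrong |

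With 4 letters per line the 1 m ceiling is 24 + 3 = 27, and the two limits fall to 27 + 10 = 37 and 27 − 10 = 17.

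**Snellen categories.** Under the same-layout assumption, one count at 1 m and at 4 m differs by a factor of 4 in letter angle, hence by 4 in the Snellen denominator. The category cannot be assigned from the count alone, even for an eye tested at 1 m at every visit.

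**Scale.** One misclassified eye is 1/145 = 0.7% of the planned sample.

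**The case against.** The strongest case against is that the error needs a change of distance, and section 20.4 asks for the same viewing distance at each visit. That does make it rarer. But it is worded as a recommendation, and it conflicts with the top-line rule in exactly the eyes that cross the limit. It also does nothing for the Snellen categories.

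A reader might infer that every eye that changes distance is misclassified, since the offset is three times the adverse-event threshold. The documents do not support that. The top-line rule caps the 1 m count, so eyes with about 44 or more letters at 4 m still fall in the right 10-letter band in either direction, although the size of the change is wrong.

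The 30 letters are not in the documents. The argument about the purpose of the switch shows that 1 m letters are angularly larger, not that they are exactly four times larger. This stands: the figure is an assumption until the layout is confirmed.

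The Visual Acuity Worksheet and the case report forms are not in the documents and might hold a conversion or a distance field. The Snellen tables presuppose some conversion. That remains possible, but the text says that what is entered is the number of correct letters.

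Section 10.3 makes the investigator responsible for identifying adverse events, so that count need not be derived from the database, and a severe loss may be noticed clinically. This too stands, although the event is defined in ETDRS letters and an investigator who applies it to the recorded counts meets the same problem.

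Finally, few eyes should be near the limit: section 8 requires potential for good acuity and excludes severe glaucoma and eyes at risk of significant vision loss. However, it sets no lower limit on preoperative BCVA, and every eye has a visually significant cataract.

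**Conclusion.** The scoring rule, followed as written, puts two scales into one variable, and this should be corrected. The offset is about 30 letters under the assumed layout, 5 letters per line and 0.1 log steps, or about 24 with 4 letters per line. A missed 10-letter loss is possible only for a worsening eye whose 4 m count was below about 44. A false 10-letter loss is possible only for an improving eye whose 4 m count is about 24 or less. Snellen categories are undetermined without the distance, whether or not it changes.

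The documents do not say how many eyes will be tested at 1 m; the number is probably small. A reader might infer that the effectiveness results are at risk. They are not: the IOP and medication endpoints and the sample size do not use BCVA, and the BCVA summaries are descriptive with no hypothesis test.

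**What to change.** 1. In section 20.4, require the test distance to be entered in the EDC with each letter count.
2. Convert all counts to one scale before any change or Snellen category is derived for 10.2 and 11.5.2. Add the chart's distance offset to 4 m counts: 30 letters once the standard layout is confirmed. State the rule in 11.5.2.
3. Reconcile the same-distance sentence in 20.4 with the top-line rule, so that sites know what to do when an eye crosses the limit.

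The cost is one CRF field, one derivation rule and the matching text edits, with no extra testing. If the distance is not captured at the visit, it may not be recoverable later.
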